2.1. PRIMARY OBJECTIVE

This is a two-part, multicentre, open label, non-randomized, phase Ib/II study to assess the safety and tolerability, MTD and preliminary efficacy of Givinostat in patients with JAK2^{V617F} positive PV.

Part A is the dose escalation portion of the Study; and, once the MTD is established, **Part B** is commenced where the preliminary efficacy of Givinostat in PV patients is to be established. Patients are enrolled either in **Part A** or **Part B** and transition from one part to the other is not allowed.

PART A

- To characterize the safety, tolerability and MTD of Givinostat in patients with PV.

PART B

- To evaluate the preliminary efficacy of Givinostat at the MTD after 3 cycles according to the clinico-haematological European LeukemiaNet (ELN) response criteria [\[1\]](#).
- To determine the safety and tolerability of Givinostat at the MTD after 3 cycles.

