3.4.3. BLINDING

No blinding procedures are applicable as the Study is open label.

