3.5. DETERMINATION OF SAMPLE SIZE

A standard 3+3 design adopting a modified Fibonacci escalation schema is used in **Part A** [3, 4, 5].

Sample size for **Part B** is discussed for the primary endpoint defined as the Overall Response Rate after 3 cycles. Simon's 2-stage design is employed in **Part B** [6] with the aim of testing the "null hypothesis" that $RR \leq 0.50$ versus the "alternative" that $RR \geq 0.75$. Response rate was assessed as defined in paragraph 6.2.5.2 of the Study protocol version 3.0. Overall, up to 28 patients are to be recruited, 12 patients being enrolled in Stage 1. PV patients enrolled at the MTD in **Part A** can be counted towards Stage 1.

Under the "null hypothesis" (if $RR = 0.50$), the expected total sample size is 18.2 patients, the probability of early termination at the end of Stage-1 is 0.613 and the probability of rejecting the "null hypothesis" is 0.081 (the target for the type-I error being 0.100).

Under the "alternative hypothesis" (if $RR = 0.75$), the probability of rejecting the "null hypothesis" in favor of the "alternative" is 0.902 (the type-II error being 0.098).

After testing the treatment on 12 patients in Stage 1, if 6 or fewer patients responded to the treatment, the trial should be terminated rejecting the "alternative" that $RR \geq 0.75$. Otherwise, the trial should go on to Stage 2 enrolling a further 16 patients to a total of 28 patients.

If at the end of Stage-2, a total of 17 or fewer patients responded to the treatment, the "alternative hypothesis" that $RR \geq 0.75$ should be rejected; alternatively, if 18 or more patients responded, the "null hypothesis" that $RR \leq 0.50$ should be rejected.

Estimations were obtained from CRO proprietary software (based on SAS® 9.2) according to the

Document: PPD

Author: PPD

Version Number:

V2.2

Version Date:

21 March 2018

Template No: CS_TP_BS016 – Revision 3

Reference: CS_WI_BS005

Effective Date: 01May2012

Copyright © 2012 Quintiles Transnational Corp. All rights reserved.

The contents of this document are confidential and proprietary to Quintiles Transnational Corp. Unauthorized use, disclosure or reproduction is strictly prohibited.

algorithm proposed by R. Simon [6].

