 6. Progression in constitutional symptoms: Appearance of constitutional symptoms.

- **Moderate response:** Complete response in anaemia with progression in splenomegaly **or** partial response in anaemia without progression in splenomegaly **or** any response in splenomegaly without progression in anaemia and constitutional symptoms.

- **Minor response:** Any leukocyte- **or** platelet-based response without progression in anaemia, splenomegaly, **or** constitutional symptoms.

- **No response:** Any response that does not qualify at least as minor response.

In all cases (PV, ET and MF patients), the disease-related systemic symptoms are evaluated directly by patients according to MPN-SAF QOL questionnaire [8, 9].

In all cases, the response status of the patient can be reviewed by a panel of independent Investigators, if necessary.

In all cases, the medical judgment of the Investigator's is taken into account. In particular, if the Investigator's clinical response assessment – that takes into account the overall medical judgment of the specific patient's case - is not in agreement with the exact application of the clinico-haematological ELN or EUMNET response criteria , the Investigator's assessment will supersede the “mathematical”

Document PPD

Author: PPD

Version Number:

V2.2

Version Date:

21 March 2018

Template No: CS_TP_BS016 – Revision 3

Reference: CS_WI_BS005

Effective Date: 01May2012

Copyright © 2012 Quintiles Transnational Corp. All rights reserved.

The contents of this document are confidential and proprietary to Quintiles Transnational Corp. Unauthorized use, disclosure or reproduction is strictly prohibited.

application of these criteria and used for analysis into study report. Also mathematical application of ELN response criteria (not agreed by the medical site team) will be analyzed.

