17.2. PART B

The following primary efficacy parameters will be evaluated in **Part B after 3 cycles of treatment** (i.e. at the end of Cycle 3) based on ITT analysis set and PP analysis set:

- **For PV and ET (if any):** Complete response (CR) and partial response (PR) rate according to clinico-haematological ELN response criteria [1];
- **For MF (if any):** CR, major response, moderate response and minor response rate according to the EUMNET response criteria [7].

Note that only in case the enrolment in **Part A** is slow (i.e. < 5 patients enrolled in 3 months, the eligibility for this part of the study could be expanded to all patients with cMPN.

The clinico-haematological ELN response criteria [1] and EUMNET response criteria will be used to assess the preliminary efficacy of Givinostat (primary endpoint) after 3 cycles of treatment in **Part B** for PV/ET and MF patients, respectively.

In all cases, the medical judgment of the Investigator's is taken into account. In particular, if the Investigator's clinical response assessment – that takes into account the overall medical judgment of the

Document: PPD

Author: PPD

Version Number:

V2.2

Version Date:

21 March 2018

Template No: CS_TP_BS016 – Revision 3

Reference: CS_WI_BS005

Effective Date: 01May2012

Copyright © 2012 Quintiles Transnational Corp. All rights reserved.

The contents of this document are confidential and proprietary to Quintiles Transnational Corp. Unauthorized use, disclosure or reproduction is strictly prohibited.

specific patient's case - is not in agreement with the exact application of the clinico-haematological ELN or EUMNET response criteria, the Investigator's assessment will supersede the "mathematical" application of these criteria and used for analysis into study report. Also mathematical application of ELN response criteria (not agreed by the medical site team) will be analyzed.

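### The Part B primary endpoint is defined by the ELN criteria, but the open-label investigator's assessment replaces the computed ELN response in any discordant case, so the stated error rates are not guaranteed for the ELN rate

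*SAP*

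**What the plan says.** - **Objective.** SAP section 2.1, Part B: "To evaluate the preliminary efficacy of Givinostat at the MTD after 3 cycles according to the clinico-haematological European LeukemiaNet (ELN) response criteria". Section 17.2 likewise names the CR and PR rate by those criteria as the primary efficacy parameter.
- **Criteria.** Section 16.3 gives the PV criteria as haematocrit below 45% without phlebotomy, platelets at most 400 x 10⁹/L, WBC at most 10 x 10⁹/L, normal spleen size and no disease-related symptoms. Partial response needs the haematocrit criterion alone, or three or more of the others.
- **Override.** Sections 16.3 and 17.2 say that if the investigator's clinical assessment disagrees with the exact criteria, it takes precedence over the mathematical "application of these criteria and used for analysis into study report. Also mathematical application of ELN response criteria" will be analysed. Sections 16.11, 18.1, 18.2 and 19.1 carry the same rule.
- **Safeguards.** Section 3.4.3: "No blinding procedures are applicable as the Study is open label". Section 16.3: "the response status of the patient can be reviewed by a panel of independent Investigators, if necessary".
- **Decision rule.** Section 3.5: "Sample size for Part B is discussed for the primary endpoint defined as the Overall Response Rate after 3 cycles". "After testing the treatment on 12 patients in Stage 1, if 6 or fewer patients responded to the treatment, the trial should be terminated"; "Otherwise, the trial should go on to Stage 2 enrolling a further 16 patients to a total of 28 patients". At the end, the alternative is rejected if "a total of 17 or fewer patients responded to the treatment". Section 17.2 evaluates the Stage 1 hypothesis on CR and/or PR at C3D28, which is the response that carries the override.
- **Parallel tables.** The revision history for V2.2 adds six Part A and ten Part B tables for the mathematical application.

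**The concern.** The objective names one quantity, the ELN response rate. The quantity counted against the cut-offs is the ELN classification where investigator and criteria agree, and the investigator's view where they do not. That view is formed without blinding and without a control arm. The SAP does not say on what grounds a classification may be overruled, whether upgrades and downgrades are treated alike, or how many are tolerable. Nor does it require adjudication of discordant cases.

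The cut-offs are tight. One reclassified patient separates 6 from 7 of 12, which decides whether Stage 2 opens, and 17 from 18 of 28, which decides whether the null hypothesis is rejected. If reclassification is not balanced, the operating characteristics in section 3.5 describe a different rate from the one named in the objective.

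**Working it through.** **Inputs from SAP section 3.5.** n1 = 12, stop if at most 6 respond; N = 28, reject the null if at least 18 respond; null rate 0.50, alternative 0.75.

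**Formulae.** With X1 ~ Bin(12, p) and X2 ~ Bin(16, p):
- P(stop at Stage 1) = P(X1 ≤ 6)
- P(success) = Σ over x = 7 to 12 of P(X1 = x) · P(X2 ≥ 18 − x)
- Expected N = 12 + 16 · (1 − P(stop))

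**Step 1: reproduce the plan.**
- At p = 0.50: P(stop) = 0.6128, expected N = 12 + 16 × 0.3872 = 18.2, P(success) = 0.0815.
- At p = 0.75: P(success) = 0.9017.

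The SAP prints 0.613, 18.2, 0.081 and 0.902. The design arithmetic is sound.

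**Step 2: what the override does to the counted rate.** If the true ELN rate is π, a share u of ELN non-responders is upgraded and a share d of ELN responders is downgraded, the counted rate is

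p = π(1 − d) + (1 − π)u.

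The SAP gives neither u nor d. The values below are assumptions.

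**Step 3: net upgrading at π = 0.50 (p = 0.50 + 0.50u).**

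| u (net) | p | P(success) | P(stop at Stage 1) |
|---|---|---|---|
| 0% | 0.500 | 0.081 | 0.613 |
| 2% | 0.510 | 0.098 | 0.585 |
| 5% | 0.525 | 0.128 | 0.544 |
| 10% | 0.550 | 0.191 | 0.473 |
| 20% | 0.600 | 0.362 | 0.335 |

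The 0.100 target is passed at u of about 2.2% (p = 0.511).

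**Step 4: one patient.** Suppose exactly one responder is added by upgrading, with a true rate of 0.50. If that happens in Stage 2, success needs X1 ≥ 7 and X1 + X2 ≥ 17, with probability 0.140. If it happens in Stage 1, success needs X1 ≥ 6 and X1 + X2 ≥ 17, with probability 0.164.

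**Step 5: net downgrading at π = 0.75 (p = 0.75(1 − d)).** With d = 5%, p = 0.7125 and power is 0.806. With d = 10%, p = 0.675 and power is 0.673.

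**Step 6: balanced overrides.** At π = 0.50 with u = d = 5%, p = 0.50 × 0.95 + 0.50 × 0.05 = 0.50, so the type I error stays at 0.081. In general, if upgrades and downgrades are equal in expected number, p = π and nothing in section 3.5 changes.

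**The case against.** **The override has no stated direction.** A reader might infer that an unblinded investigator mainly turns borderline failures into partial responses, so that the type I error is inflated. The document does not show that. The rule applies to disagreement either way, no frequency is given, and balanced or absent overrides leave the error rates as stated. This objection stands, which is why the figures are an assumed range and downgrading is shown beside upgrading.

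**The computed ELN rate will be reported.** The V2.2 tables place it beside the investigator-assessed rate, so a reader of the report can compare the two. This stands, and it softens the consequence. It does not settle which rate is set against the cut-offs.

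**The criteria are not fully programmable as written.** Section 16.11 only recommends that sites supply local normal spleen values, and section 10 says splenectomised patients have no spleen evaluation. Section 16.3 lists microvascular disturbances as a symptom, but the questionnaire items listed in section 10 include none of that name. A score of 0 is tied to symptom absence only in section 19.1. This stands, and any programmed primary analysis must close these gaps. The haematocrit route to partial response is fully numeric.

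**Section 3.5 does not itself say ELN.** It takes its response definition from protocol paragraph 6.2.5.2, which is not available here. A reader might infer that the hypotheses are expressly stated for the ELN rate, or that the override departs from the protocol. Neither can be confirmed. The link to ELN rests on sections 2.1 and 17.2, which is enough for the point.

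**The trial is mainly for estimation.** Section 6.5 says so, and efficacy is called preliminary. Even so, the Stage 1 stopping decision and the final rejection rule both use the response count.

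**Conclusion.** The point holds in this form. The Part B primary endpoint is named as an ELN response rate, yet in every discordant case the value counted is the unblinded investigator's, with no limit on use and only optional independent review. The computed ELN rate is reported in parallel but has no role in either Simon decision. The type I error of 0.081 and power of 0.902 are therefore no longer guaranteed for the ELN rate.

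The size depends on an override frequency and direction that the SAP does not give. On the assumed range of 5% to 20% net upgrading at a true ELN rate of 0.50, success has probability 0.128 to 0.362 and the futility stop 0.544 to 0.335. About 2.2% net upgrading uses up the margin between 0.081 and the 0.100 target. In the other direction, 5% to 10% net downgrading at a true 0.75 lowers power to between 0.806 and 0.673. The calculation treats patients as independent with a common rate. It does not show that bias occurred, or which way it would run.

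**What to change.** In SAP sections 16.3, 16.11, 17.2, 18.1, 18.2 and 19.1, exchange the roles of the two analyses:

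1. The programmed ELN response is the main analysis. For the Part B primary endpoint it is the one used for both the 7/12 and the 18/28 decisions. In section 16.11 and the matching part of section 19.1, the same applies to the revised ELN criteria.
2. The investigator-assessed response is the sensitivity analysis.
3. Add a listing of every discordant patient with the computed response, the investigator's response, the direction of change and the reason.
4. State how the spleen component is derived (which local normal values apply, and how splenectomised patients are classified) and how the symptom component is derived (which MPN-SAF items count, and what score counts as absent).

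The cost is SAP wording, a short derivation rule and one listing. The mathematical tables are already planned, and the sample size and cut-offs do not change. The headline response rate may be less favourable.

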3.3. PART B

Part B is a multicentre, open label, non-randomized, phase II, cohort expansion Study to assess the preliminary clinical efficacy of Givinostat at the MTD in patients with JAK2^{V617F} positive PV.

Patients enrolled in **Part B** started at the MTD defined in **Part A** (i.e. 100 mg b.i.d.), according to an optimized Simon's 2-stage design [\[6\]](#).

The dose of Givinostat is modified for Study protocol specified toxicities (see [paragraph 4.3.3.2](#) of the Study protocol version 3.0).

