7. STATISTICAL CONSIDERATIONS

7.1. ADJUSTMENTS FOR COVARIATES AND FACTORS TO BE INCLUDED IN ANALYSES

No adjustment for covariates will be performed for this study.

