Frequency and percentage of patients in each response category (CR, PR, no response (NR) for PV and ET; CR, major response, moderate response, minor response and NR rate for MF) will be presented at Cycle 3 Day 28 (C3D28). Of note, patients who dropped the study due to drug-related TEAE(s) before that the post-baseline efficacy measurement is obtained (i.e. at C3D28 and/or at C6D28), the post-baseline efficacy measurements (i.e. at C3D28 and/or at C6D28) will be considered as "No Response*", even if these assessments were not performed. "*" will allow to distinguish them from them from the therapeutic response evaluation result of "No Response", that will be reported without "*" (i.e. "No Response"). Other missing data will not be replaced, if not otherwise specified.

For **Part B** – Stage 1, Simon's design hypothesis will be evaluated by calculating the frequency and 95% CI of patients with a CR and/or PR at C3D28.

For Part B – Stage 2, the efficacy of Givinostat will be evaluated by means of a generalized linear model (logit link function and binomial distribution) adjusting for age, sex and disease type (PV, ET, MF). The therapeutic response will be collapsed in two categories in order to improve the model performance:

- For PV and ET:
 - a) "Responders" (i.e. CR and PR), and
 - b) "Not Responders" (i.e. NR);
- For MF:
 - a) "Responders" (i.e. CR, major response, moderate response and minor response), and
 - b) "Not Responders" (i.e. NR for MF).

In addition, the following primary safety parameters will be evaluated in **Part B after 3 cycles of treatment** (i.e. at the end of Cycles 3, or including data related to Cycles 1, 2 and 3) based on SAF analysis set:

- Number of patients experiencing AEs.
- Type, incidence, and severity of treatment-related AEs, graded according to CTCAE v. 4.03 (14th June 2010).

AEs will be coded using MedDRA dictionary (using the 20.1 version). AEs will be reported on a per patient basis. If a patient has more than one AE for a treatment that is coded to the same PT, the patient will be counted only once for that PT. Similarly, if a patient has more than one AE for a treatment within a SOC category, the patient will be counted only once in that SOC category. A patient with multiple CTCAE grades for an AE will be summarised under the maximum CTCAE grade recorded for the event.

Document: PPD

Author: PPD

Version Number:

V2.2

Version Date:

21 March 2018

Template No: CS_TP_BS016 – Revision 3

Reference: CS_WI_BS005

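### Section 17.2 evaluates Part B Stage 2 efficacy with an adjusted logistic model that contradicts section 7.1, carries a constant covariate and does not apply the 18-of-28 rule of section 3.5

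*SAP*

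**What the plan says.** Section 3.5 sets a Simon two-stage design for the response rate (RR) after 3 cycles, testing RR of 0.50 or less against 0.75 or more: "Overall, up to 28 patients are to be recruited, 12 patients being enrolled in Stage 1". The trial stops at Stage 1 "if 6 or fewer patients responded to the treatment". The final rule is also a count: "If at the end of Stage-2, a total of 17 or fewer patients responded to the treatment", the alternative is rejected, and 18 or more responders reject the null. The stated operating characteristics are a type I error of 0.081 ("the target for the type-I error being 0.100") and power of 0.902 ("the type-II error being 0.098"). Section 4 describes the final analysis as Stage 2 of this Simon design.

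Section 17.2 specifies the primary efficacy analysis in three steps:
- It tabulates the response categories at Cycle 3 Day 28 (C3D28), without limiting the table to one stage.
- For Stage 1, it evaluates the Simon hypothesis by the frequency and 95% interval of CR and/or PR.
- For Stage 2, it says that "the efficacy of Givinostat will be evaluated by means of a generalized linear model (logit link function and binomial distribution) adjusting for age, sex"; a third covariate is disease type, with levels PV, ET and MF. It names no contrast, null value or significance level, and does not mention 18 of 28.

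Section 7.1 states: "No adjustment for covariates will be performed for this study". Section 3.3 defines Part B as a "cohort expansion Study to assess the preliminary clinical efficacy of Givinostat at the MTD in patients with JAK2^{V617F} positive PV". Sections 3.1 and 3.2 let only PV patients from Part A at the chosen dose count towards Part B, and section 3.1 confines any widening to other neoplasms to Part A. Section 6.5 provides a two-sided 95% interval for the primary endpoint, by Normal approximation or exact method, and profile-likelihood intervals for model parameters.

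**The concern.** Section 17.2 is where a programmer or report author looks for the primary analysis. It ties Stage 1 to the Simon hypothesis and then moves to a regression model at Stage 2, with no link back to the count rule. The model breaks the SAP's own general rule on covariates, contains a factor that cannot vary in Part B, and yields no quantity that section 17.2 compares with 0.50.

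At stake is which result carries the Part B efficacy conclusion. The trial is open label, and the count rule, a 95% interval and a model-based test can disagree near the boundary. A plan that leaves the model's role undefined leaves room to choose among them after the data are seen. The error rates quoted in section 3.5 hold only if the count rule is the one used.

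**Working it through.** **1. Reproduce the design figures.** Inputs from section 3.5: n1 = 12, stop at 6 or fewer; n = 28, reject RR ≤ 0.50 at 18 or more; p0 = 0.50, p1 = 0.75.

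- Early termination under the null: P(X1 ≤ 6 | 12, 0.50) = 2510/4096 = 0.6128 (stated 0.613).
- Expected N: 12 + 16 × (1 − 0.6128) = 18.20 (stated 18.2).
- Rejection probability: sum over x = 7 to 12 of P(X1 = x) × P(X2 ≥ 18 − x), with X2 binomial on 16 patients. At p = 0.50 this is 0.0815 (stated 0.081). At p = 0.75 it is 0.9017 (stated 0.902).

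The arithmetic in section 3.5 is right, and a search over designs with type I error at most 0.10 and power at least 0.90 returns the same design as Simon-optimal. These figures describe the count rule and nothing else.

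**2. Is there a term that tests 0.50?** Part B has one arm, so there is no treatment coefficient. Since logit(0.50) = 0, the only related parameter is the intercept. With age and sex in the model, uncentred, it is the log-odds at age 0 in the reference sex, not the overall RR. As an illustration, covariates were assumed because the SAP gives none: age mean 60, SD 10; sex 50:50; both unrelated to response. With exactly 18 of 28 responders in each of 2,000 draws, the probability implied by the intercept ran from about 0.01 to 0.997 (5th to 95th percentile).

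**3. Can disease type be estimated?** With every patient PV, the design matrix of intercept, age, sex and a disease-type indicator has 4 columns and rank 3. Disease type is aliased with the intercept.

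**4. How far could other criteria depart from the count rule?**

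| Responders of 28 | Rate | Count rule | Exact 95% CI | Normal-approximation lower limit |
|---|---|---|---|---|
| 17 | 0.607 | does not reject | 0.406 to 0.785 | 0.426 |
| 18 | 0.643 | rejects | 0.441 to 0.814 | 0.465 |
| 19 | 0.679 | rejects | 0.476 to 0.841 | 0.506 |
| 20 | 0.714 | rejects | 0.513 to 0.868 | 0.547 |

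Even a logistic model with no covariates differs from the count rule. At 18 responders, z = ln(18/10) / √(1/18 + 1/10) = 0.588/0.394 = 1.49, two-sided p = 0.136. At 19, p = 0.065. At 20, z = 2.19, p = 0.029.

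Keeping the Stage 1 rule and changing only the final bar:
- 18 or more: type I error 0.0815, power 0.9017.
- 19 or more (Normal-approximation interval excludes 0.50): 0.041 and 0.843.
- 20 or more (exact interval, or the intercept-only Wald test, excludes 0.50): 0.017 and 0.741.

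**The case against.** The strongest reply is that the SAP already answers the primary question. Section 3.5 gives the threshold, section 4 calls the final analysis Stage 2 of the Simon design, the C3D28 table in section 17.2 supplies the count, and section 6.5 supplies an interval. Section 17.2 never says that the model replaces the rule. This stands. A reader might infer that the primary efficacy question goes unanswered, or is answered only by a model that cannot answer it. The document as a whole does not support that, because a decision rule is prespecified and its inputs are planned. What remains is that section 17.2 does not apply the rule at Stage 2 and gives the model no defined role beside it.

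Second, the intercept's meaning depends on coding, which the SAP does not state. Centred covariates or a standardised estimate would give a related quantity. That is fair, but neither is specified, and a covariate-adjusted intercept is still conditional rather than the overall rate.

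Third, a constant disease-type term does no numerical harm, since the age and sex fit is unchanged. Also true: it looks like text carried over from the conditional wording for ET and MF, and it is not a source of bias. It still cannot be fitted as specified.

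A reader might also infer a real risk of separation from the small number of non-responders (28 × 0.25 = 7 expected at RR 0.75, or 3.5 per slope for age and sex). That count supports a warning about imprecision. It does not establish separation, and the SAP gives no covariate distribution from which to derive its frequency.

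**Conclusion.** The point holds in this form. The Stage 2 analysis in section 17.2 is wrong as written on three counts: it contradicts section 7.1, it includes a covariate that is constant under sections 3.1 to 3.3, and it specifies no contrast that tests RR ≤ 0.50. The SAP nevertheless contains a valid final rule, so the consequence is two unreconciled Stage 2 evaluations rather than a missing one.

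The size is confined to the boundary. At 18 responders the count rule rejects while both interval methods include 0.50. At 19 the exact interval still includes 0.50 and the Normal approximation does not. If an interval or Wald criterion displaced the rule, power would fall from 0.902 to between 0.741 and 0.843, and type I error from 0.081 to between 0.017 and 0.041. These figures assume 28 evaluable patients and an unchanged Stage 1 rule. They show how far the criteria can differ; the SAP does not say that an interval or Wald test will decide. The intercept illustration rests on assumed covariates. The contradiction and the constant covariate need no assumptions.

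**What to change.** - In section 17.2, state that the primary Stage 2 test is the Simon count rule on C3D28 responders (CR or PR): reject RR ≤ 0.50 if at least 18 of 28 respond. Cross-refer to section 3.5.
- Report the response rate with one named interval method and call the interval descriptive. Say that the count rule governs, and that a two-sided 95% interval can include 0.50 when the rule rejects (exact method at 18 and 19 responders, Normal approximation at 18). Remove the open choice of method in section 6.5 for this endpoint.
- Delete disease type from the model.
- Either drop the age and sex model, or label it exploratory and state what it estimates.
- Align section 7.1: leave it as it is if the model is dropped, or add the exploratory exception if it is kept.

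The cost is SAP wording, with at most one model removed or moved to the exploratory outputs. No data collection, sample size or design figure changes.
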